#### Considerations for pituitary gland contouring

Pituitary dysfunction is a known complication from brain tumor radiation therapy. Approximately 41% of adult brain tumor survivors, at an average age of 6 years after radiation exposure, have evidence of some degree of hypopituitarism, including 16% with a single hormonal deficiency, 25% with multiple deficiencies and 7% with panhypopituitarism. While patients with glioblastoma rarely survive to six years, it is still important to consider radiation-induced hypopituitarism (RIH) as a potential complication.

Typically, doses of 50-54 Gy using standard fractionation are given to low grade brain tumors, including pituitary tumors, with known (RIH) as a complication. For higher doses of radiotherapy given to suprasellar tumors such as craniopharyngiomas, RIH is more common, suggesting both a possible dose or dose-volume correlation to the side effect. Investigators have suggested that doses above approximately 40-42 Gy are associated with RIH in patients receiving standard fractionation (1.8-2.0 Gy per fraction). Single fraction radiosurgery has been used to treat secretory and non-secretory pituitary tumors and suprasellar tumors.

This protocol involves the use of hypofractionated radiotherapy with a regimen of 45 Gy delivered in 15 fractions (3 Gy per fraction). Typically, dose-fractionation comparisons are preformed using biologic

CONFIDENTIAL

This material is the property of the NYU School of Medicine. Do not disclose or use except as authorized in writing by the study sponsor

equivalent dose (BED) calculations. This makes use of an alpha-beta ratio (typically assumed to be 3 for tumors and 10 for normal tissue). For 45 Gy delivered in 15 fractions, alpha/beta of 3 yields an equivalent dose of 54 Gy and alpha/beta ratio of 10 yields an equivalent dose of 49 Gy at 2 Gy per fraction. Given that we do not know the alpha-beta of pituitary tissue with certainty and that RIH is associated with doses above 40 Gy at 2 Gy / fraction, it is reasonable to set a dose constraint for the pituitary gland.

A reasonable constraint would be to contour the pituitary gland and set the maximum point dose at 45 Gy (no more than 3 Gy per fraction) in order to lower the risk of RIH.

#### **5.2.2.3 Technical Factors (Equipment, Energies)**

Intensity modulated radiotherapy (IMRT) via any method (e.g., VMAT, static field IMRT) or Stereotactic Radiotherapy (SRT) is required. Any FDA cleared external beam radiation delivery system may be used (including conventional linear accelerators, cyberknife systems, tomotherapy, proton therapy, etc.). Treatment at NYU SoM will be on a Varian LINAC (TrueBeam or Edge), or Elekta Gamma Knife Perfexion Unit.

Image-guided radiotherapy with cone-beam CT along with daily treatment kV/kV imaging will be performed daily.

Imaging for treatment planning will be obtained with the patient in the same position and immobilization device as for treatment. All patients will be positioned via a combination of rigid immobilization and daily image guidance to ensure positioning accuracy of 3 mm or better, and of a magnitude that justifies the PTV margin applied.

#### **5.2.2.4 Localization, Simulation, and Immobilization**

MRI fusion with CT are required for treatment planning. At least 1 of these scans must be of the patient immobilized in treatment position, and with image resolution of no worse than 1.5 mm x 1.5 mm x 3 mm. MRI sequences should include axial T1 post-contrast stereotactic image (such as MP-RAGE or FSPGR BRAVO). Additionally, a T2 sequence (e.g., FLAIR or T2, preferably stereotactic, thin slice, contiguous) is helpful to identify any non-enhancing tumor.

Immobilization must be rigid (e.g., thermoplastic masks). For daily treatment, localization will include the steps of a) immobilization with the same device used for simulation, and b) daily image guidance using at a minimum orthogonal pairs of radiographs aligned to DRRs as a computer-assisted process. Daily cone-beam CT will be used as well.

#### **5.2.2.5 Treatment Planning/Target Volumes**

A GTV will be defined using the simulation CT scan. Fusion of the pre- and post-operative MRI scans are fused to the CT simulation scan for target delineation.

The GTV includes the post-operative resection cavity if no residual enhancing or non-enhancing tumor is noted. The GTV also includes surrounding T2/FLAIR abnormality. A CTV represents the GTV plus a 1-2 cm margin respecting normal anatomic boundaries. Care is made to not include any enhancement or T2 signal on the post-operative scan that is due to post-surgical infarct.

A PTV expansion that is justified based on image guidance and immobilization will be applied. The PTV margin is typically 3-5 mm. Daily cone-beam CT scans will be used prior to each treatment to guide radiation therapy.

#### **5.2.2.6 Critical Structures**

Normal tissues to be contoured will include the brain, brainstem, optic nerves and chiasm. Planning risk volume (PRV) expansions the same size as the PTV expansion (e.g. If the PTV is 3 mm, then the PRV is 3 mm.) should be utilized for optic nerves and chiasm.

CONFIDENTIAL

This material is the property of the NYU School of Medicine. Do not disclose or use except as authorized in writing by the study sponsor

Special consideration should be given to limit the exit dose through the oral cavity and mucosa.

The treatment parameters should be modified to optimize the conformity of the prescription isodose volume to the target volume while minimizing dose to critical structures. OAR limits for newly diagnosed GBM are given in **Table A2**.

**Table A2: Normal Dose Limits for Newly Diagnosed GBM (15 Fractions)**

Dose Metric	Per Protocol	Deviation Unacceptable
Maximum Dose (0.03 cc) to PRV for Optic Nerves, Chiasm	Less than or equal to 40 Gy photons	Greater than 40 Gy photons
Maximum Dose (0.03 cc) to Brainstem	Less than or equal to 45 Gy photons	Greater than 45 Gy photons

Coverage of the PTV will be decreased in order to fulfill these limits.

The optic structures (chiasm and optic nerves) are kept to <267 cGy per fraction and the brainstem is allowed a maximum dose (0.03 cm) of less than or equal to the prescription dose of 45 Gy.

#### **5.2.2.7 Documentation Requirements**

At the completion of treatment, the following should be forwarded to the overall Principal Investigator listed below. Investigators must submit the following information:

- Daily treatment record.
- Radiotherapy summary.
- Pre-study CT or MRI (the Scan used to delineate the target volumes for planning. Submit the entire series and specify which one was used for planning).
- Isodose distributions displayed on orthogonal planes or, if not possible, on multiple transverse slices through each target.

Data should be submitted to:

[name], PhD  
Laura and Isaac Perlmutter Cancer Center  
NYU School of Medicine  
[name]  
[name]

### **5.3 Administration of Study Drugs**

#### **5.3.1 Nivolumab and Ipilimumab Preparation and Dosing**

Nivolumab and ipilimumab must be prepared in the site investigational pharmacy. Preparation of the diluted Nivolumab and ipilimumab for administration must be accomplished by adequately trained personnel to guarantee the sterility of the product to be injected. Only clinical site personnel who are appropriately trained on the procedure detailed in this document may perform the preparation and administration procedures. Clinical site personnel involved in these procedures must comply with all applicable regulations and standards. The administration must be performed by adequately trained personnel. Prior to dosing the subject, adhere to normal standard of care and aseptic techniques. Utilize local site procedures as appropriate.

CONFIDENTIAL

This material is the property of the NYU School of Medicine. Do not disclose or use except as authorized in writing by the study sponsor

Refer to the IB and/or package inserts for complete instructions for specific nivolumab and ipilimumab handling instructions, dose calculation, reconstitution, preparation of the infusion fluid, and administration.

**Setting:** Nivolumab and ipilimumab will be administered in an outpatient setting as intravenous (IV) infusions; however, inpatient administration is permitted. Nivolumab and ipilimumab should be administered in a setting that allows for immediate access to an intensive care unit or equivalent environment and administration of therapy for anaphylaxis, such as the ability to implement immediate resuscitation measures. Steroids (dexamethasone 10 mg), epinephrine (1:1,000 dilution), allergy medications (IV antihistamines), bronchodilators, or equivalents, and oxygen should be available for immediate access. If an acute infusion reaction is noted, subjects should be managed according to Section 6.2.8

Nivolumab 3 mg/kg IV will be given as a 30-minute infusion every 2 weeks ( $\pm 3$  days of the scheduled day of drug administration).

Ipilimumab 1 mg/kg IV will be given as a 30-minute infusion every 6 weeks ( $\pm 5$  days of the scheduled day of drug administration).

Dosing calculations should be based on the body weight assessed. If the subject's weight on the day of dosing differs by  $> 10\%$  from the weight used to calculate the prior dose, the dose must be recalculated. All doses should be rounded up or to the nearest milligram per institutional standard.

There will be no dose escalations or reductions allowed.

Subjects may be dosed with nivolumab no less than 18 days from the previous dose. Subjects may be dose with ipilimumab no less than 37 days from the previous dose.

Doses of nivolumab and/or ipilimumab may be interrupted, delayed, or discontinued depending on how well the subject tolerates the treatment. Dosing visits are not skipped, only delayed. See Section 6.2 for dose delay and discontinuation criteria.

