#### **Safety Lead-In/Main Study Cohort:**

On C1D8, seven days after nivolumab and ipilimumab administration, all subjects will be administered radiotherapy (RT) to a total dose of 45 Gy, given in 15 consecutive fractions of 3 Gy each fraction.

On C1D15, subjects will receive nivolumab 3 mg/kg IV. Thereafter, nivolumab administration will continue once every 2 weeks.

On C2D1, subjects will receive ipilimumab 1 mg/kg IV. Thereafter, ipilimumab administration will continue once every 6 weeks.

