and nivolumab for Grade  $\geq 3$  amylase and lipase abnormalities that are not associated with symptoms or clinical manifestations of pancreatitis and that are attributed to ipilimumab alone.

- Nivolumab may be delayed until the next planned ipilimumab dose if the next ipilimumab dose is scheduled within the next 18 days. This will permit periodic ipilimumab dosing to be synchronized with nivolumab dosing.
- Ipilimumab should be dosed at the specified interval regardless of any delays in intervening nivolumab doses. However, in order to maintain periodic synchronized dosing of ipilimumab and nivolumab, the dosing days of nivolumab and ipilimumab may be adjusted within the permitted  $\pm 5$  day window, as long as consecutive nivolumab doses are given at least 16 days apart. Ipilimumab may be delayed beyond the 5 day window if needed to synchronize with the next nivolumab dose.
- If an ipilimumab dose is delayed beyond 6 weeks from the prior ipilimumab dose, then subsequent ipilimumab doses should rescheduled to maintain the 6-week interval between consecutive ipilimumab doses.
- A dose delay of ipilimumab which results in no ipilimumab dosing for  $> 12$  weeks requires ipilimumab discontinuation, with exceptions as noted in Section 6.2.4.2.

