- Research blood samples. All subjects will have the below research blood samples collected. Note: Research blood samples will be taken at only 2 timepoints: **Cycle 1, Day 1 (pre-dose)** and **Cycle 2, Day 1** (end of week 6).
  - A total of 40 mL (four 10 mL purple top EDTA tubes) of whole blood will be drawn and immediately sent to the below sites:
    - One (1) 10 mL tube will be sent to the Center for Biospecimen Research and Development (CBRD) at NYUSoM for acquisition of whole blood, buffy coat, and plasma samples.
    - Three (3) 10 mL tubes will be sent to the Immune Monitoring Core (IMC) at NYUSoM and immediately processed for isolation of PBMCs.

**Study Drugs:** Nivolumab and ipilimumab will be administered in an outpatient setting as an IV infusion at the specified doses (for details see Administration of Study Drugs, Section 5.3). The day of the first nivolumab and ipilimumab infusion will be designated as Cycle 1, Day 1.

The doses of study drug must be adjusted each cycle for changes in body weight of  $\geq 10\%$ . The weight used for dosing can be taken within 3 days of scheduled study drug administration.

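### Section 5.3.1 sets an 18-day minimum between nivolumab doses that cannot be reconciled with the 2-weekly schedule in the same section

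*Combined protocol and SAP*

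**What the plan says.** Section 5.3.1 gives the routine schedule: "Nivolumab 3 mg/kg IV will be given as a 30-minute infusion every 2 weeks", with a window of 3 days on either side. Later in the same section come two minimum intervals. For nivolumab: "Subjects may be dosed with nivolumab no less than 18 days from the previous dose". For ipilimumab, which is given every 6 weeks with a 5-day window: "Subjects may be dose with ipilimumab no less than 37 days from the previous dose". Neither sentence is limited to delayed or resumed treatment.

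The visit schedule follows the 2-week interval. For the Main Study Cohort, Section 3.1.3 says: "On C1D15, subjects will receive nivolumab 3 mg/kg IV. Thereafter, nivolumab administration will continue once every 2 weeks". Section 6.4.1 fixes the starting point: "The day of the first nivolumab and ipilimumab infusion will be designated as Cycle 1, Day 1". Section 6.4.3 allows 3 days either side of the C1D15 visit, which is a nivolumab-only visit.

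The Surgical Study Cohort (Sections 3.1.3, 6.1.3 and 6.5) receives its first dose on C1D-29, has surgery up to 2 weeks later, and receives its second nivolumab dose on C1D1, 2 weeks after surgery. From C1D15 nivolumab is given every 2 weeks.

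Three related figures do not agree:

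- Section 6.2.3 lets dosing days be moved to synchronise the two drugs "as long as consecutive nivolumab doses are given at least 16 days apart". Section 6.2.3.2 gives 18 days for the same purpose.
- Section 5.2.1 counts 2 nivolumab doses in a 42-day cycle. The synopsis and Sections 3.1.3, 6.1, 6.4.1 and 6.5 count 3.

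**The concern.** A minimum interval is an operative dosing limit: pharmacy and clinic staff are expected to refuse a dose that comes too early. Here the limit is longer than the scheduled interval, so the two instructions cannot both be followed.

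Staff must break one of them. If they keep to the calendar, on-schedule doses contradict a written limit, and monitors checking adherence under Section 10.1 would have grounds to query them. If they keep to the limit, subjects receive nivolumab less often than the regimen under test. In neither case does the protocol state a usable shortest interval, which is the safety purpose of such a sentence.

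**Working it through.** **Inputs.** Nivolumab interval 14 days, window ±3 days, minimum 18 days (5.3.1). Ipilimumab interval 42 days, window ±5 days, minimum 37 days (5.3.1). Full course 96 weeks, or 16 cycles (5.2.1): 96 × 7 = 16 × 42 = 672 days.

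**1. How the ipilimumab figure arises.** Interval minus window: 42 - 5 = 37. This reproduces the stated minimum exactly. The same rule for nivolumab gives 14 - 3 = 11, not 18. Even the latest in-window gap after a fixed first dose, 14 + 3 = 17, is below 18.

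**2. Main Study Cohort, dose 1 to dose 2.** Dose 1 is Day 1 by definition and so cannot move. Dose 2 is Day 15 + d, with d from -3 to +3. The gap is 14 + d: 11, 12, 13, 14, 15, 16 or 17 days. None of the seven permitted days reaches 18.

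**3. Surgical Study Cohort, dose 1 to dose 2.** Nominal gap: 14 days to surgery plus 14 days after it, or 28 days. The earliest case under 6.5.2 and 6.5.3 is surgery at 7 days and the dose 14 - 3 = 11 days later, and 7 + 11 = 18. This gap complies. The next one, C1D1 to C1D15, is 14 days as scheduled and does not.

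**4. Later 2-weekly gaps, windows fixed to the original calendar.** With offsets a and b, each from -3 to +3, the gap is 14 + (b - a).

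- Range: 14 - 6 = 8 to 14 + 6 = 20 days.
- Gaps of 18 or more need b - a of at least 4: 3 + 2 + 1 = 6 of the 49 combinations.
- On the scheduled days (a = b = 0) every gap is 14 and breaches.
- Two consecutive gaps span at most 28 + 6 = 34 days; two compliant gaps need 2 × 18 = 36. They cannot both comply.

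This uses the routine ±3-day window. If the ±5-day synchronising adjustment in 6.2.3 were used for the last of the three doses, the span would be 28 + 3 + 5 = 36, which only just reaches the requirement.

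**5. If the scheduled day moves with the previous dose instead.** Every gap is then at most 14 + 3 = 17 days, and no 2-weekly gap complies. The documents do not say which reading applies.

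**6. Doses if 5.3.1 is followed literally (Main Study Cohort, first dose on day 0 of 672).**

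| Gap | Last dose day | Doses |
|---|---|---|
| 14 days | 47 × 14 = 658 | 48 |
| 18 days | 37 × 18 = 666 | 38 |

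Shortfall: 48 - 38 = 10 doses; 10/48 = 20.8%.

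Section 3.1.3 expects about 10 months of participation. Taking that as 304 days (an assumption), the counts are 22 (last dose day 21 × 14 = 294) and 17 (last dose day 16 × 18 = 288): 5 fewer, or 5/22 = 22.7%.

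**7. Doses per cycle.** 42/14 = 3, not the 2 stated in 5.2.1.

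**The case against.** The best defence is that the 18 days was meant only for doses being delayed or synchronised, as in 6.2.3 and 6.2.3.2. Those sections do attach that condition to their own minimums. The sentence in 5.3.1 does not: it stands with the routine schedule and is paired with an ipilimumab minimum that is plainly a routine one. Nor would the condition reach C1D15 in the Main Study Cohort, where no ipilimumab dose is due and there is nothing to synchronise.

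A second defence is that the 2-week calendar is repeated so often that sites will follow it and no doses will be lost. That is probably right, and it makes the dose shortfall largely hypothetical. The written limit would still be breached routinely.

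A third is that the 96-week comparison describes few subjects. Section 1.1.1 cites 6% two-year survival in this population with existing treatment, and Section 3.1.3 expects about 10 months on study. This stands for the absolute number of doses; the proportion is similar over 10 months.

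Finally, an 11-day floor would itself rule out gaps of 8 to 10 days that the ±3-day windows allow. That is true, and it is why the sponsor has to choose the figure.

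**Conclusion.** The contradiction is real and lies within one section. In the Main Study Cohort no in-window second dose can meet the 18-day minimum. In both cohorts every 2-weekly gap given on schedule breaches it. Literal compliance would mean at most 38 instead of 48 doses over a full 96-week Main Study Cohort course, about 21% fewer; the likelier outcome is routine breach of a written limit. The statement about two consecutive gaps assumes ±3-day windows fixed to the original calendar. Sample size, alpha and power are untouched.

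A reader might infer more than the documents support:

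- **That the second dose can never comply, or that every gap in the trial breaches.** A second dose delayed for toxicity under 6.2.3 can fall at 18 days or later, though it is then outside its window. The first gap in the Surgical Study Cohort complies.
- **That keeping nivolumab aligned with ipilimumab every 42 days would cost a still larger share of doses.** That is one scenario only. Section 6.2.3 also says: "Ipilimumab may be delayed beyond the 5 day window if needed to synchronize with the next nivolumab dose". Alignment could therefore be kept by stretching ipilimumab instead.
- **That the figures were carried over from a 3-weekly nivolumab regimen.** The documents say nothing about their origin.

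**What to change.** - **5.3.1:** replace 18 days with a minimum that fits dosing every 2 weeks ±3 days. Eleven days (14 - 3) follows the construction of the ipilimumab figure. The sponsor should confirm that it intends to bar the 8 to 10 day gaps that a late dose followed by an early one would otherwise allow.
- **6.2.3 and 6.2.3.2:** state one synchronisation minimum compatible with 2-weekly dosing, in place of 16 and 18 days.
- **5.2.1:** change the nivolumab count per 42-day cycle from 2 to 3.
- **6.2.3, check only:** a separate 18-day figure governs when nivolumab may wait for ipilimumab ("Nivolumab may be delayed until the next planned ipilimumab dose if the next ipilimumab dose is scheduled within the next 18 days"). It is not a minimum interval, but it should be reviewed in the same pass.

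The cost is wording in four places, in one amendment, plus a sponsor decision on the minimum. No design parameter or analysis changes.

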### 5.3.2 Nivolumab and Ipilimumab Administration

**When study drugs (nivolumab and ipilimumab) are to be administered on the same day, nivolumab is to be administered first.** Nivolumab infusion must be promptly followed by a saline flush to clear the line of nivolumab before starting the ipilimumab infusion.

**The second infusion will always be ipilimumab** and will start after the infusion line has been flushed, filters changed, and patient has been observed to ensure no infusion reaction has occurred. The time in between infusions is expected to be approximately 30 minutes but may be more or less depending on the situation.

Separate infusion bags and filters should be used when administering nivolumab and ipilimumab on the same day.

There are no premedications recommended for nivolumab or ipilimumab.

**Nivolumab** Injection, 100 mg/10 mL (10 mg/mL) is to be administered as an IV infusion through a 0.2-micron to 1.2-micron pore size, low-protein binding (polyethersulfone membrane) in-line filter at the protocol-specified doses. It is not to be administered as an IV push or bolus injection. Nivolumab injection can be infused undiluted (10 mg/mL) or diluted with 0.9% Sodium Chloride Injection, USP or 5% Dextrose Injection, USP to protein concentrations as low as 0.35 mg/mL. Instructions for dilution and infusion of nivolumab injection are provided in the IB and/or package insert. Care must be taken to assure sterility of the prepared solution as the product does not contain any antimicrobial preservative or bacteriostatic agent.

CONFIDENTIAL

This material is the property of the NYU School of Medicine. Do not disclose or use except as authorized in writing by the study sponsor

Nivolumab infusions are compatible with polyvinyl chloride (PVC) or polyolefin containers and infusion sets and glass bottles.

Ipilimumab injection can be used for IV administration without dilution after transferring to a PVC, non-PVC/non-DEHP or glass container and is stable for 24 hours at 2-8°C or room temperature/ room light (RT/RL). For ipilimumab storage instructions, refer to ipilimumab IB and/or package insert.

Ipilimumab is to be administered as a 30-minute IV infusion, using a volumetric pump with a 0.2 to 1.2 micron in-line filter at the protocol-specified dose. The drug can be diluted with 0.9% normal saline or 5% Dextrose Injection to concentrations between 1 mg/mL and 4 mg/mL. It is not to be administered as an IV push or bolus injections. Care must be taken to assure sterility of the prepared solutions, since the drug product does not contain any antimicrobial preservatives or bacteriostatic agents. At the end of the infusion, flush the line with a sufficient quantity of normal saline or 5% dextrose solution.

Subjects should be carefully monitored for infusion reactions. Vital signs should be obtained before, after infusion and in-between ipilimumab and nivolumab infusions. If an acute infusion reaction is noted, subjects should be managed according to Section 6.2.8.

